While evidence in the literature is scant, there is no clear consensus on the need and efficacy of heparinized saline as the solution for maintaining patency in implanted port catheters (Camp-Sorrell, 2010). The investigators in this study examined the community standard, which revealed that while some area hospitals do use heparin in the final flush solution for implanted port

catheters, others adopted a saline only flush practice. This practice change does not appear to be based on evidence in the literature or the results of their own research. However, they do report anecdotally that there has been no increase in the use of alteplase (CathFlo: a thrombolytic) since the practice change.

The purpose of this study is to determine the safest and most effective flushing solution(s) for maintaining patency in implanted port catheters. The researchers also hope to conclude that the complication rate in patients whose ports are flushed with saline only is no greater than those of patients whose ports are flushed with the combination of saline and heparinized saline. These complications might include partial or complete obstruction, infection of the central line, and/or the onset of heparin induced thrombocytopenia.

Research Question(s):

- 1. Does a saline only flush maintain the patency of implanted port catheters at a rate comparable to a heparinized saline solution?
- 2. Is there any difference in the type and rate of complications among implanted port catheters flushed with saline versus heparinized saline?

Null Hypothesis:

We are proposing a non-inferiority trial. Thus, the null hypothesis is: Implanted port catheters flushed with saline only will experience an occlusion rate of more than 10% over the occlusion rate experienced in implanted port catheters flushed with a heparinized saline solution.

The alternative hypothesis is: Implanted port catheters flushed with saline only will experience an occlusion rate less than 10% over the occlusion rate experienced in implanted port catheters flushed with heparinized saline solution.

Background Information/Literature Review:

Care of Implanted Port Catheters at TriHealth

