Based on the literature and our own experience we estimated an approximate occlusion rate of 20% with the standard treatment (saline + heparinized saline flush as described above). The power analysis conducted by [name] determined that, using a two-group normal approximation test of proportions with a one-sided .05 significance level, a sample size of 198 participants per group will have 80% power to reject the null hypothesis that the proposed method is not inferior (i.e. the difference in proportions between the proposed method and the standard method is greater than 0.10). Thus, we will continue data collection until 198 have been completed in each group for a total of 396 study participants who completed 6 months of data collection. To date (July 3, 2019), 69.7% of patients enrolled in the study are able to complete 6 months of data collection without withdrawing for an exclusion criterion (ex: transferring to hospice, being started on an anticoagulant, etc). Therefore, we plan to consent 575 patients to result in 396 who complete the study. Once 396 patients have completed 6 months of data collection will stop and any remaining active participants will be withdrawn from the study.

Data Collection:

Independent Variables: Method for flushing implanted port catheters:

• 20 mL of saline followed by 5 mL of Heparinized saline in a concentration of 100 units/mL

OR

• 20 mL of saline only

Dependent Variables:

Primary Outcomes

- Occurrence of first complete (can neither withdraw blood nor flush the catheter) occlusion
- Occurrence of first partial (able to flush but unable to withdraw blood) occlusion
- Frequency with which alteplase (CathFlo) has to be utilized to resolve an occlusion

Secondary Outcomes

- Number of subsequent occurrences of complete or partial occlusions after the first occurrence.
- Amount of time in days that a port remains patent (flushes easily and able to obtain a blood return).
 - Amount of time between entrance in study and first incidence of partial or complete occlusion
 - Amount of time between incidences of partial or complete occlusion.
- Occurrence of other complications:
 - Central Line-Associated Blood Stream Infection (CLABSI) a laboratory-confirmed (recognized pathogen cultured from one or more blood cultures; organism cultured from blood is not related to an infection at another site) blood stream infection that is considered central line associated (CDC, 2012).
 - Develops complication related to Heparin

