Statistical Analysis: Descriptive statistics will be used to describe the participants. Differences between groups on the dependent variables will be calculated using t-test, Chi-Square or Fisher's exact test as appropriate for the level of data under analysis (also see discussion regarding interim analysis). Regression analysis will be used to determine the effect of the moderating variables on the occurrence of occlusion in the implanted ports. Participants in the control group and intervention group will be further stratified based on frequency of port flushing. Differences in the rate of occlusion between stratified groups will also be calculated.

Ethical Considerations: The purpose of this study is to determine the safest and most effective flushing solution(s) for maintaining patency in implanted port catheters. In so doing, study participants could be placed at potential risk for catheter occlusion. All catheter occlusion will be treated according to the site's policy, i.e., the instillation of alteplase (CathFlo) (see Appendix A). Potential study participants will be made aware of

the risk when enrolled in the study (See Appendix B (V.2, 2-20-2015) script for recruiting patients into the study and Appendix F, the Informed Consent Statement).

- **Informed Consent:** Patients who meet inclusion criteria will be approached by a member of the research team who will explain the study, implications of their participation and review the Informed Consent Statement and HIPAA Authorization Form(s) (see Appendix F and G). Participants will receive a copy of the signed Informed Consent Statement and HIPAA Authorization. The original signed Informed Consent Statement and HIPAA will be stored in a locked cabinet at a TriHealth office or locked location at UCMC, or an off-site locked storage area, for six years after the study is closed at which time the documents will be destroyed via mechanical shredder.

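### The hoped-for conclusion that complications are no greater with saline goes further than a 10-point non-inferiority test of occlusion, or a plain difference test of line infection, can support

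*Combined protocol and SAP*

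**What the plan says.** **Aim.** The Purpose of Study section says what the researchers hope to find: "the complication rate in patients whose ports are flushed with saline only is no greater than those of patients whose ports are flushed with" both solutions. It then explains the term: "These complications might include partial or complete obstruction, infection of the central line, and/or the onset of heparin induced thrombocytopenia". The hoped-for statement therefore covers occlusion as well as infection and HIT (heparin-induced thrombocytopenia).

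**Hypotheses.** The Null Hypothesis section proposes a non-inferiority trial. Its alternative, with the heparinized saline group as comparator, is narrower than the aim: "Implanted port catheters flushed with saline only will experience an occlusion rate less than 10% over the occlusion rate experienced in implanted port catheters". The sample-size text at the end of the Recruitment section expresses the null as a case where "the difference in proportions between the proposed method and the standard method is greater than 0.10", and the test is specified as "using a two-group normal approximation test of proportions with a one-sided .05 significance level", with 198 per group and 80% power. The interim-analysis text sets the final level at 0.0471.

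**Other complications.** Research question 2 asks: "Is there any difference in the type and rate of complications among implanted port catheters flushed with saline versus heparinized saline". The Data Collection section lists CLABSI and heparin-related complications as secondary outcomes. The Statistical Analysis section assigns t-tests, chi-square or Fisher's exact tests of difference to the dependent variables. It gives no margin and no confidence interval for any complication other than occlusion, and it plans no interval for occlusion either.

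**The concern.** The aim is worded as a zero-difference claim, while the occlusion test is built to rule out an excess of 10 points or more. A result that passes the test may still be compatible with saline being several points worse. For CLABSI the gap is wider. The only planned analysis is a test of difference, so the only support it could give for *no greater* is a failure to reach significance, and that does not show absence of an excess.

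The literature review says the study is meant to inform practice recommendations, and the background section describes catheter-related thrombus and bacteremia as potentially life-threatening. A headline that drops the margin would tell readers more about safety than the trial had established.

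**Working it through.** **Inputs.** From the documents: control occlusion rate 20%, margin 0.10, one-sided alpha 0.05, power 80% and 198 per group (Recruitment); final level 0.0471 (Experimental Aspect of the Study); HIT in 1–5% of heparin-exposed patients (Background). Assumed here: equal true rates when reproducing the sample size; an unpooled normal-approximation limit for the occlusion difference; all CLABSI rates.

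**1. The plan's own figure.**
n = (z₀.₉₅ + z₀.₈₀)² × [p₁(1−p₁) + p₂(1−p₂)] / margin²
= (1.645 + 0.842)² × (0.16 + 0.16) / 0.10² = 197.8, rounded up to **198 per group**.
The stated size is reproduced. The design is sized for a 10-point margin.

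**2. Largest observed excess that still passes.** Non-inferiority is met when d + z × SE < 0.10, with SE = √{[p_c(1−p_c) + p_s(1−p_s)]/198} and z = 1.674 for level 0.0471. With 40/198 (20.2%) occlusions on heparin:

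| Saline | d | SE | Upper limit | Passes? |
|---|---|---|---|---|
| 46/198 (23.2%) | 0.0303 | 0.0414 | 0.0996 | yes |
| 47/198 (23.7%) | 0.0354 | 0.0416 | 0.1049 | no |

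The test is met with an observed excess of up to 6/198, about 3.0 points.

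**3. Chance of passing when saline is truly worse.** P(pass) = Φ[(0.10 − true difference)/SE − 1.674].
- True 25% v 20%: SE = √[(0.16 + 0.1875)/198] = 0.0419. Then 0.05/0.0419 − 1.674 = −0.480, which gives **32%**. Exact binomial enumeration also gives 32%. In about 19% of all such trials the test passes with saline observed to be worse.
- True 22% v 20%: the same formula gives 61%.

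Both cases lie inside the stated alternative, so passing is a correct decision under the plan. It becomes wrong only if reported as *no greater*.

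**4. CLABSI.** The documents give no rate, so a range is shown for 198 per group. Power is for a two-sided Fisher test at 0.05, by exact enumeration. The bound is the one-sided 95% limit when both groups show the same observed rate r: 1.645 × √[2r(1−r)/198].

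| Assumed rate, heparin v saline | Power to detect the doubling | Bound at equal observed rates (r = heparin rate) |
|---|---|---|
| 1% v 2% | 4% | 1.6 points |
| 2% v 4% | 13% | 2.3 points |
| 3% v 6% | 22% | 2.8 points |
| 5% v 10% | 40% | 3.6 points |

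Across this range a true doubling would go undetected in 60% to 96% of trials.

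**5. HIT, for contrast.** If HIT does not occur with saline (an assumption), Fisher's test is significant from 6 v 0 events (p = 0.030). Power is then 2% at a 1% rate with heparin, 21% at 2%, 55% at 3%, 81% at 4% and 93% at 5%.

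**The case against.** The strongest reply is that the sentence is an aspiration in a purpose section. The operative text is properly framed: the trial is declared as non-inferiority, the hypotheses carry the 10-point margin, the first research question asks only for a comparable rate, and the sample-size and interim texts repeat the margin. All of this stands, so the point is a mismatch between aim and test and not an error in the design.

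Several stronger readings are tempting, and the documents do not support them:

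- **That a reporting rule is in place.** A reader might infer that a positive test will be announced as *no greater*, or that a non-significant CLABSI result will be read that way. No section says so. Equally, no section ties the phrase to the margin or rules that reading out.
- **That 32% is a false-positive rate.** It is not. A true 25% v 20% meets the stated alternative, and any non-inferiority design will pass some true excesses inside its margin.
- **That occlusion and HIT will be pooled, so one harm hides the other.** The singular *complication rate* invites this, but no such composite is defined. The outcome lists keep occlusion, CLABSI, HIT and other heparin allergy apart. The interim text combines only partial with complete occlusion, and the final analysis also takes those two separately.
- **That the trial has no power for HIT.** Over the document's own 1–5% range, power runs from very low to 93% if saline has none. The expected direction also favours saline, so HIT is not where a false reassurance would arise.

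What remains is the gap between the wording and the analysis for occlusion and CLABSI.

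**Conclusion.** The concern holds, limited to occlusion and CLABSI. A positive occlusion result would support an excess of less than 10 points and nothing stronger. It can be reached with saline observed about 3 points worse, and about 32% of the time when saline is truly 5 points worse. For CLABSI, a non-significant difference would be weak evidence of no excess at every rate considered.

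The occlusion figures assume a 20% control rate, 198 analysed per group, a normal-approximation limit at 0.0471, and no allowance for the interim looks. The CLABSI figures rest wholly on assumed rates. Only their direction, which is the same across the range, should be relied on.

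**What to change.** 1. In Purpose of Study, replace the *no greater* wording with: the occlusion proportion with saline only is less than 10 percentage points above that with heparinized saline.
2. In Statistical Analysis, add the saline-minus-heparin difference with a confidence interval for occlusion, for CLABSI and for heparin reactions, each reported separately.
3. For CLABSI, state the largest excess that the interval does not exclude, and say that a non-significant difference will not be read as showing no excess.

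This costs a change of wording and a few interval estimates from data already collected. No patients are added, and the margin, hypotheses and sample size stay as they are. The downside is a slightly less favourable headline.

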Setting for the Study: TCI Infusion Centers, specifically: the TCI Good Samaritan (GS) Infusion Center at GSH; the TCI GS Infusion Center Butler County; the the TCI GS Infusion Center at the Thomas Center; the TCI GS Infusion Center, Cheviot; the TCI GS Infusion Center, Medicenter; the TCI GS Infusion Center, Anderson; and the McCullough Hyde

Memorial Hospital infusion center. In January 2018, University of Cincinnati Medical Center Barrett Infusion Center was added as a data collection site.

Participants: Patients receiving care in the identified settings who have an implanted port catheter will be recruited to participate in this study.

Inclusion Criteria:

- over the age of 18 years
- able to read and understand English
- has an implanted port in place less than one (1) year
- evidence of a patent port catheter prior to enrollment in the study
- is receiving active treatment i.e., receiving a therapeutic drug through the implanted port
- current treatment protocol projected to continue for a minimum of three (3) months
- anticipates receiving care at the identified centers for 6 months following enrollment in the study
- receives routine care of the implanted port catheter at any of the identified data collection sites

Exclusion Criteria:

- has documented Heparin platelet antibody (could not be randomized to either group) or other allergy to Heparin
- receiving therapeutic dose of an anticoagulant, i.e., warfarin, heparin, enoxaparin, etc.
- has a heparin-coated port (for example BioFlo port)
- does not meet one or more of the inclusion criteria

Recruitment

Prospective study participants will be identified the day prior to their appointment in the treatment center by a member of the research team. Their chart will be reviewed for inclusion criteria and flagged as a potential study participant.

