When the potential study participant arrives in the treatment center, a member of the research team will escort the patient into a treatment room and explain the study by reading a prepared script (see Appendix B). If the patient expresses interest, the Informed Consent Statement and HIPAA Authorization form will be reviewed and signed. After obtaining informed consent, a participant will be randomly assigned to the heparinized saline flush (control group) or saline only flush study group (intervention group). A color-coded sticker will be placed on the patient's treatment folder indicating participation in the study and group assignment. The random assignment process will be achieved using sequentially-numbered opaque sealed envelopes (SNOSE) containing the group assignment. A yellow colored data collection face sheet (see Appendix C) will indicate control group; a blue colored data collection face sheet will indicate the intervention group.

During FY 2012, 391 patients with implanted port catheters were treated in the OPCC. Seventy of these patients experienced an occlusion of their port that required the administration of alteplase (CathFlo) ([name], personal communication, October 12, 2012). Thus, 70 of 391 experienced an occlusion resulting in an occlusion rate of 18%. Some of these 70 patients experienced an occlusion more than once during that time. Additionally, during that time, a few patients had their implanted port catheters removed due to infection or malfunction. The exact number of patients who experienced multiple occlusions or had their implanted ports removed/replaced during FY2012 is unknown.

We engaged the consultation of a biostatistician through the Center for Clinical and Translational Science and Training (CCTST) to conduct a power analysis to establish the number of participants needed in each group to determine the non-inferiority of the alternative therapy (saline only flush). Consultation was provided by [name], Associate [name] Hospital Medical Center, University of Cincinnati.

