 - HIT (Heparin induced thrombocytopenia as measured by a positive HIT antibody test)
 - Other heparin allergy

Moderating variables: other things that could also affect patency of the port

- Number of times port flushed per month or frequency of flushing.
- Use of prophylactic doses of anticoagulant drugs (e.g., enoxaparin, heparin, warfarin)
- Development of a hypercoaguable state, as diagnosed by primary hematologist/oncologist
- Mechanical difficulties related to port placement e.g. "Pinch-off syndrome"
- Length of time port has been in place prior to entrance in study

Extraneous variables:

- Type of cancer
- Age of participant

Data collection tool

The data collection tool (see Implanted Port Catheter Flushing Data Collection Form – Face Sheet: Appendix C and Record of Flushes: Appendix D) were developed by the principal and sub-investigators specifically for the purpose of this study. The tool was reviewed by the OPCC nurses for completeness and clarity. In addition to basic demographic information (age, gender), the nurse will record the patient's type of cancer, and the diagnosis or history of any hypercoaguable state or use of anticoagulant medication as documented in the patient chart. The nurse will also document the type of implanted port catheter (single/double), the port location (right/left, subclavian vein (described in the operative note or chest x-ray), and the date the port was inserted so that length of time the port has been in place can be calculated. Data will be recorded on the Face Sheet when the patient is enrolled in the study and as pertinent information/events become known, i.e., as complications occur.

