Potential risks for study participants in either arm of the study include partial occlusion (can instill flush solution but not withdraw blood) and complete occlusion (can neither instill flush solution nor withdraw blood). Study participants could require removal of the port if an occlusion cannot be resolved, and possibly require re-insertion of a new implanted port. In the event of any occlusion, alteplase (CathFlo) in the policy established dose and frequency (see Appendix A) will be instilled to resolve the occlusion. Study participants whose implanted ports are found occluded on three (3) consecutive visits to the treatment center will be excluded from further data collection, i.e., their participation in the study will be terminated. The standard flushing as prescribed by the site's policy or as prescribed by the attending physician will be used. Study participants whose occlusion cannot be resolved with alteplase and require removal of the port will also be terminated and excluded from further data collection. Patients who develop port infections necessitating port removal will be terminated and excluded from further data collection. Study participants who develop HIT (heparin induced thrombocytopenia) or other heparin allergy will be terminated and excluded from further data collection. Likewise, patients who have thrombotic or embolic phenomenon requiring therapeutic anticoagulation will be terminated and excluded from further data collection. If a participant in the intervention group receives clinical care and their port is flushed with heparin (following standard hospital policy), the participant will be withdrawn from the study.

The study will be closed if there is evidence that study participants in the intervention arm experience implanted port occlusion at a disproportionate rate. The amount of alteplase (CathFlo) used in each group will be assessed each

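### Randomised participants are withdrawn when they later meet an exclusion criterion, and the planned proportion tests have no safe way to handle the roughly 30% with truncated follow-up

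*Combined protocol and SAP*

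**What the plan says.** Assignment comes straight after consent (Recruitment): "After obtaining informed consent, a participant will be randomly assigned to the heparinized saline flush (control group". Exclusions that arise later are therefore post-randomisation events.

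The sample-size text in the same section gives the completion rate as 69.7%, meaning patients who reach six months "without withdrawing for an exclusion criterion (ex: transferring to hospice, being started on an anticoagulant, etc". It plans 575 consents and sets the end of the trial by completers: "we will continue data collection until 198 have been completed in each group for a total of 396 study participants". Anyone still active at that point is withdrawn.

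The termination list under Experimental Aspect of the Study covers these grounds only in part. It does not name hospice transfer, and it ends participation for anticoagulation only after a clotting event: "patients who have thrombotic or embolic phenomenon requiring therapeutic anticoagulation will be terminated and excluded from further data collection". Starting an anticoagulant for another reason appears only in the sample-size text.

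The Exclusion Criteria bar patients "receiving therapeutic dose of an anticoagulant", while the moderating variables include "Use of prophylactic doses of anticoagulant drugs (e.g., enoxaparin, heparin, warfarin".

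The Data collection tool section already provides for noting "use of anticoagulant medication as documented in the patient chart", and it allows for later events: "Data will be recorded on the Face Sheet when the patient is enrolled in the study and as pertinent information/events become known".

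Statistical Analysis lists the t-test, chi-square and Fisher's exact test for group differences. It does not say who is analysed or how a participant with less than six months of follow-up is scored.

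**The concern.** Entry criteria decide who may be randomised. Using them afterwards to remove people breaks the comparison that randomisation set up, unless removal has nothing to do with occlusion. Anticoagulation and end-of-life transfer could plausibly be related to clotting risk or to how often the port is used. Staff also know the allocation from coloured stickers and face sheets.

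The practical difficulty is in the analysis. A chi-square or Fisher test needs a yes or no for each participant over a common period, and about three in ten will not have that period. Two uses are natural:

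- **Completers only.** The comparison is then made in a group selected after randomisation.
- **Everyone, scored on what was seen.** A participant who left at two months without an occlusion counts as occlusion-free at six. Both arms' rates fall, and so does the absolute difference between them. In a non-inferiority trial with an absolute margin, that favours the saline-only claim.

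At stake is whether a finding within the 10-point margin reflects the flush solution or the way incomplete follow-up was scored.

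**Working it through.** **Inputs from the protocol.** Control occlusion rate 20%, margin 0.10, one-sided 0.05, 80% power, 198 per group, completion 69.7%, 575 consents (Recruitment); final-analysis alpha 0.0471 (interim analysis text).

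**1. The plan's own figures.** With equal true rates of 20% (my assumption for the saline arm), n = (1.645 + 0.842)² × (0.20 × 0.80 + 0.20 × 0.80) / 0.10² = 197.8, so 198 per group. This matches. For consents, 396 / 0.697 = 568.1, so 569 against the stated 575, about 1% apart. The sample-size arithmetic is sound.

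**2. Size of the loss.** 1 − 0.697 = 0.303, and 575 × 0.303 = 174. The documents give no breakdown by reason or arm.

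**3. Everyone counted, truncated follow-up scored as occlusion-free.** Assumptions: true six-month rates of 30% saline and 20% control (the boundary of the null), about 287 per arm (575 / 2), the same 30.3% loss in both arms, and non-completers showing half their six-month risk before leaving.

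- Share of risk observed: 0.697 + 0.303 × 0.5 = 0.8485.
- Observed rates: 0.30 × 0.8485 = 0.2546 and 0.20 × 0.8485 = 0.1697. Difference 0.0849.
- SE = √[(0.2546 × 0.7454 + 0.1697 × 0.8303) / 287] = 0.0339.
- Chance of declaring non-inferiority = Φ[(0.10 − 0.0849) / 0.0339 − 1.674] = Φ(−1.23) = 0.110.

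The nominal rate is 0.0471. If non-completers show three-quarters of their risk, the same steps give a difference of 0.0924 and 7.3%. At one quarter they give 0.0773 and 16.3%. Interim looks are ignored throughout.

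**4. Completers only.** Same true rates, 198 completers per group, and the same selection in both arms. Let L = 0.303, and let s be the share of the loss due to later exclusion criteria (assumed 10%, 25% or 50%, that is 17, 44 or 87 of 575). Other loss, U = L(1 − s), is unrelated to occlusion. Would-be occluders leave for these reasons r times as often as others, so d = Ls / (pr + 1 − p). The completer rate is p(1 − U − rd) / [p(1 − U − rd) + (1 − p)(1 − U − d)].

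Example with s = 0.50 and r = 1.5: the rates become 0.2802 and 0.1842, the difference 0.0960, SE 0.0422, and Φ(0.096 − 1.674) = 0.057.

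| r | s = 10% | s = 25% | s = 50% |
|---|---|---|---|
| 1 | 4.7% | 4.7% | 4.7% |
| 1.5 | 4.9% | 5.2% | 5.7% |
| 1/1.5 | 4.5% | 4.2% | 3.8% |

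Under equal selection the effect is small and can run either way.

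**5. Dilution from retaining participants.** If all of share s were retained, they would be w = Ls / (1 − L + Ls) of those analysed: 4.2% at s = 10% and 17.9% at s = 50%. Suppose the flush difference is halved in them, with control at 20% and 198 per group. The difference is 0.10 × (1 − w/2) = 0.0979 or 0.0911, and false non-inferiority is 5.2% or 7.1%. This overstates the cost of the fix to the extent that s includes hospice leavers, who cannot be followed at a site.

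**The case against.** **The plan never says completers only.** A reader might infer such an analysis from the completer-based sizing and stopping rule. The documents do not support that: no passage drops occlusions seen before withdrawal, and the termination text bars only further data collection. This stands, so the point cannot rest on a completers-only analysis. It rests on both natural uses of the named tests being exposed.

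**The selection effect is small.** Under equal selection, false non-inferiority moves only between 3.8% and 5.7%. This stands. Much larger figures can be produced by assuming that the whole 30.3% loss is tied to occlusion in the saline arm alone, but nothing in the documents supports that, and the same approach can also yield a rate well below nominal.

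**The anticoagulant dose is not ambiguous.** A reader might think the sample-size text removes anyone on any anticoagulant. But it refers to an exclusion criterion, the only such criterion concerns a therapeutic dose, and prophylactic use is kept as a moderating variable. The three places agree.

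**The termination list need not be exhaustive.** Hospice transfer can fall under the catch-all exclusion for no longer meeting the inclusion criteria, and further terms may be in pages not available here. This is fair, but it does not alter the follow-up problem.

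**Stopping at therapeutic anticoagulation is defensible, since it affects patency directly.** It is, as one analysis. It does not require ending observation of a participant whose port is still accessed at a study site.

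**Conclusion.** The concern holds in a limited form. The protocol removes randomised participants for criteria met later, expects about 30% non-completion, and names only fixed-time tests, with no rule for shortened follow-up. Scoring truncated participants as occlusion-free has a known direction when the null is true: towards non-inferiority. Its illustrated size is a difference of about 8.5 points and a false-claim rate of about 11% against 4.7%. That rests on the half-risk assumption, equal loss by arm, a normal approximation and no interim looks. Completers-only selection could run either way and was small in the cases tried.

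The bias in the trial itself cannot be sized, because reasons, timing and arm of withdrawal are not given. Loss unrelated to occlusion would leave a completers-only comparison unbiased, but would not prevent the shrinkage in step 3. The sample-size arithmetic is not in question. The change should be made before the final analysis.

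**What to change.** 1. State that entry criteria apply at enrolment only. For a participant who starts a therapeutic anticoagulant but still has the port accessed at a study site, keep completing the Record of Flushes to month 6, and note the start date and reason on the Face Sheet. Amend the anticoagulation item in the termination list to match.
2. Analyse all randomised participants in their assigned group, counting every occlusion recorded before withdrawal. Compare six-month first-occlusion proportions by Kaplan-Meier, with a confidence interval for the difference set against the 10% margin. Those who leave site care, for example to hospice, contribute up to that date. This assumes that leaving is unrelated to occlusion within each arm, so the reasons must be visible.
3. Report alongside it a supportive analysis that censors at anticoagulant start or departure from the assigned flush, and tabulate withdrawals by group and reason.

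**Cost.** A short amendment and brief staff retraining; the forms exist and are already in use. These participants must stay enrolled, because the sheets are kept in the folder only for current participants. Enrolment was under way by July 2019 and earlier withdrawals may not be recoverable, so follow-up rules will be mixed; numbers before and after the change should be reported. Retained anticoagulated participants may dilute the difference somewhat (step 5), which is why the supportive analysis is needed.
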